### 10.3.3. Safety analysis

Safety analysis will be summarized on the Safety Population (i.e. all patients who receive any part of investigational treatment).

Extent of exposure to study drug will be summarized by treatment group, using descriptive statistics. Duration of study treatment will be calculated in days and presented in months as the date of the last dose of any study treatment – date of the first dose of any study treatment + 1. Dose modification will be summarized. Patients who discontinue study drug or are removed from the study prematurely will also be reported. Reasons for study drug therapy discontinuation, and time of withdrawal from the study will be described.

Incidence of AEs will be summarized by system organ class and preferred term according to MedDRA coding, and will be presented by treatment groups and overall. AEs will be summarized by grade (NCI-CTCAE v5.0), according to the worst grade experienced.

To adjust for unequal lengths of study treatment duration among subjects, and potentially between treatment groups, an additional summary based on event rate per 100-subject years of treatment duration will also be summarized, if necessary. The event rate per 100-subject years of treatment duration is calculated as the total number of treatment emergent events divided by the total treatment duration per 100-subject years.

Serious AE and deaths will be provided in a listing. All adverse events resulting in discontinuation, dose modification, dose interruption, and/or treatment delay of study drug will also be listed and tabulated by preferred term.

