#### STATISTICAL ANALYSIS:

For primary and secondary efficacy endpoints, the analysis will be performed on the ITT population, i.e. all randomised patients will be included, whether eligible or not, compliant or not. Patients will be analysed according to their randomisation arm, regardless of the actual treatment received.

Analysis of the primary endpoint will be event-driven. Time to event endpoints will be reported using the Kaplan-Meier method with Rothman's 95% confidence intervals. A log-rank test will provide the statistical significance of the randomised treatment effect. Additionally a Cox model will provide an estimate of the randomised treatment effect (hazard ratio).

Stratification factors will include: LATITUDE risk criteria (high risk versus low risk, [Fizazi, 2017](#)) and ECOG performance status score (0 or 1 vs. 2).

Qualitative data will be expressed as percentages and compared between the treatment groups using the chi-square test (or the Fisher exact test). Quantitative data will be expressed as means and standard deviation (or medians and range) and compared between the treatment groups using the Student t-test (or the Wilcoxon test).

The analysis of the secondary endpoints will be performed using a formal adjustment for multiple testing.

One interim analysis will be performed after observing at least 70% of the number of expected events (i.e. at least 138 events). Stopping rules using the spending function approach of Lan and DeMets with O'Brien-Fleming type spending function will be followed to conclude at each sequential analysis.

Nominal p values for overall type I error of 0.05 Lan-DeMets boundaries are:

- Efficacy interim analysis (138 events, i.e. 70% expected events): p-value to reject  $H_0 \leq 0.015$  (equivalent to the stopping boundaries Z-Scale:  $\pm 2.437$ )
- Final analysis (197 events, i.e. 100% expected events): p-value to reject  $H_0 \leq 0.045$  (equivalent to the stopping boundaries Z-Scale:  $\pm 2.0$ )

The results of the interim analyses will be given only to the IDMC members.

Safety analysis will be summarized on the Safety Population (i.e. all patients who receive any part of investigational treatment). Incidence of AEs will be summarized by system organ class and preferred term according to MedDRA coding, and will be presented by treatment groups and

overall. AEs will be summarized by grade (NCI CTCAE v5.0), according to the worst grade experienced.

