### **8.1.3. Adverse Event Reporting**

All AEs that occur from the time the informed consent form is signed until 30 days after the last dose of IMP must be recorded by the investigator in the patients' medical file and reported in the eCRF (see Section [Erreur ! Source du renvoi introuvable.](#) for the reporting requirements of AEs which meet any serious criteria). The investigator will make every attempt to follow all AEs until resolution and to report their outcome in the eCRF.

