### 10.1. Statistical hypothesis and sample size determination

The primary evaluation criterion/endpoint for this study is radiographic progression-free survival (Section 3.2.1).

Assuming a median rPFS of 12 months for the control group, a planned sample size of 300 subjects will be required to provide an 85% power to detect at least a HR of 0.65 (median rPFS 12 months in the standard arm versus 18.5 months in the experimental arm) at a 2-tailed significance level of 0.05 and a drop-out hazard rate in both arms of 0.014 (i.e. a maximum 19.3% drop-out rate at the end of study corresponding to non-evaluable or study withdrawal patients).

The number of **randomised patients will be 300 patients** (150 patients per arm). The dropout rate will be monitored during the study and in case of increased drop-out the sample size may be adjusted accordingly.

Based on the randomization rates observed since the inclusion of the first patient and the projected rates according to the opening of investigator sites (see below), patient inclusion-randomisation is expected to be complete in 60 months.

	Number of randomized patients during the period	Cumulative number (cumulative percentage) of randomized patients at the end of the period
March 2022-Feb 2023	18 pts (1.5 pts/months)	18 (6%)
March 2023-Feb 2024	50 pts (4.167 pts/months)	68 (22.67%)
March 2024-Feb 2025	53 pts (4.4 pts/months)	121 (40.33%)
Mars 2025-Feb 2027*	179 pts (7.5 pts per month)*	300 (100%)*

\*Grounded on projections

An additional 15 months following termination of accrual (i.e. a total of 75 months since the randomization of the first patient) is expected to obtain the required 197 events, assuming that events will follow an exponential distribution with a constant hazard rate.

The final analysis is scheduled 10 years after the last patient inclusion-randomisation.

 Based on data from the control arm of the LATITUDE trial (Fizazi, 2017), and taking into account that (i) patients with oligo-metastatic disease (low risk patients) will not be enrolled, and (ii) some patients are expected to die from other causes before they reach a progression endpoint, making the median rPFS probably shorter than that seen in the LATITUDE trial

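### Section 10.3.3 makes exposure-adjusted AE rates optional with no trigger, although the design hypothesis itself predicts about 23–31% longer exposure on darolutamide

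*Protocol*

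**What the plan says.** Section 10.3.3, like the statistical part of the Protocol summary, states: "Incidence of AEs will be summarized by system organ class and preferred term according to MedDRA coding", by treatment group and by worst grade. This carries no condition. Section 10.3.3 then recognises that treatment duration may differ between patients and between arms, and adds that "an additional summary based on event rate per 100-subject years of treatment duration will also be summarized, if necessary". The rate is defined as "total number of treatment emergent events divided by the total treatment duration per 100-subject years", with duration running from first to last dose. The Protocol summary does not mention the rate.

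Three other provisions fix how long AEs can be observed:
- Section 7: study treatment continues until radiographic progression in both arms.
- Section 8.1.3: "All AEs that occur from the time the informed consent form is signed until 30 days after the last dose of IMP must be recorded". After that, Section 7.5 collects only ongoing AEs and new treatment-related ones.
- Section 10.1: the design hypothesis is "median rPFS 12 months in the standard arm versus 18.5 months in the experimental arm".

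Safety is a key secondary objective (Section 2.2) and toxicity a key secondary endpoint (Section 3.2.2).

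**The concern.** If darolutamide delays progression as hypothesised, patients on that arm stay longer on study drug and are watched longer for AEs. A crude proportion then mixes the effect of the drug on the AE with the length of the window. The trial expects this imbalance whenever it succeeds, yet the protocol leaves the adjusted summary to a judgement with no stated rule, which could be made after the AE data are seen.

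The population is frail men, in whom events such as fractures and cerebrovascular disorders also occur on ADT alone and accumulate with time. Section 1.4.1 lists both as potential risks of darolutamide. The benefit-risk conclusion for this group could be blurred by an excess that reflects only longer observation.

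**Working it through.** **Inputs (Section 10.1).** Medians 12 and 18.5 months; HR 0.65; 150 patients per arm; drop-out hazard 0.014, read as per month; accrual of 18, 50, 53 and 179 patients in months 0–12, 12–24, 24–36 and 36–60; analysis at month 75; exponential event times.

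**Reproducing the plan first.** The protocol states that "a planned sample size of 300 subjects will be required to provide an 85% power" "at a 2-tailed significance level of 0.05". The Schoenfeld formula gives 4(1.960 + 1.036)²/(ln 0.65)² ≈ 194 events, and the Freedman formula gives 200. The stated 197 lies between them, with Schoenfeld power 85.6%. The accrual table with month-75 cut-off and drop-out gives 196.7 events and 19.8% drop-out, against 197 and 19.3% stated. The model therefore represents the plan.

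**Mean time on treatment.** Let λ be the progression hazard, d the hazard of stopping for other reasons, and F the time from entry to the cut-off. Mean time on treatment is the average over entry times of [1 − exp(−(λ+d)F)]/(λ+d), with λ = ln2/12 = 0.0578 per month on placebo and 0.65 × 0.0578 = 0.0375 on darolutamide.

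| Case | Placebo (months) | Darolutamide (months) | Ratio |
|---|---|---|---|
| d = 0.014 (plan) | 12.44 | 15.78 | 1.27 |
| d = 0 | 14.60 | 19.15 | 1.31 |
| d = 0.03 (assumed: more stopping for other reasons) | 10.58 | 13.03 | 1.23 |

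At the 138-event interim the ratio is 1.21 to 1.23. Adding one month for the 30-day AE window gives 1.25 (d = 0.014) and 1.29 (d = 0) at month 75.

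**Crude incidence of an AE with the same constant hazard in both arms.** For an assumed 12-month risk r, h = −ln(1−r)/12. On-treatment incidence is the average over entry times of h/(λ+d+h) × [1 − exp(−(λ+d+h)F)]. The documents give no AE rates for this population, so r is varied.

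| Assumed 12-month risk | Placebo, d = 0.014 | Darolutamide, d = 0.014 | Ratio, d = 0.014 | Ratio, d = 0 | Ratio, d = 0.03 |
|---|---|---|---|---|---|
| 5% | 5.1% | 6.4% | 1.258 | 1.297 | 1.223 |
| 10% | 10.0% | 12.4% | 1.247 | 1.284 | 1.214 |
| 20% | 19.2% | 23.5% | 1.226 | 1.257 | 1.197 |
| 30% | 27.8% | 33.5% | 1.205 | 1.232 | 1.181 |
| 50% | 43.4% | 50.6% | 1.166 | 1.184 | 1.149 |

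**The same AE as a rate.** At r = 10%, h is 0.105 per year. Exposure is 150 × 12.44/12 = 155.5 subject-years on placebo and 197.3 on darolutamide. Expected events are 16.4 and 20.8, that is 10.5 per 100 subject-years in each arm. The rate ratio is 1.00, where the crude ratio is 1.25.

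**The 30-day tail.** Suppose events up to 30 days (0.986 months) after the last dose enter the numerator while the denominator stops at the last dose. The rates then rise by factors of 1 + 0.986/12.44 = 1.079 and 1 + 0.986/15.78 = 1.062. The darolutamide-to-placebo ratio moves by 1.062/1.079 = 0.984, about 1.6%.

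**The case against.** The strongest reply is that Section 10.3.3 already sees the problem. It names unequal treatment duration, defines a rate for it, and tabulates extent of exposure and discontinuation by arm unconditionally. A team facing a 27% exposure gap would presumably judge adjustment necessary, and details of AE displays ordinarily belong in the SAP, which is not at hand. This largely stands and limits the point's weight. It does not supply the missing trigger: the protocol's own hypothesis already says the adjustment will be needed, so nothing is gained by leaving it open.

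Other objections also stand in part:
- **Size.** Sections 5.6 and 7.4 allow stopping for toxicity, by patient or investigator decision, or after clinical progression. None of this is in the 0.014 drop-out hazard, and it would probably narrow the gap.
- **Constant hazard.** The assumption suits fractures better than early-onset complaints such as fatigue, for which the distortion is smaller.
- **Other views of the outcomes.** Symptomatic fractures also enter symptomatic skeletal events, analysed from randomisation by log-rank test and Cox model. Fatigue is followed with the QLQ-C30.

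Three stronger readings are tempting, and the documents do not support them:
- A reader might infer that any inert drug would look harmful. A drug with no effect on rPFS gives HR 1, equal exposure and no artefact. The point needs a drug that delays progression and leaves the AE in question unchanged.
- A reader might infer an inflated false-positive rate for AE comparisons. Section 10.3.3 plans summaries, not AE tests. Only a general sentence in the Protocol summary on comparing qualitative data by chi-square could be read that way.
- A reader might infer that the planned rate is badly constructed. Total events over exposure is a legitimate descriptive rate, the protocol does not fix whether treatment-emergent covers the 30-day tail, and the possible mismatch is immaterial at about 1.6%.

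**Conclusion.** The point holds as a cheap improvement to the safety plan. Crude incidence is unconditional and the exposure-adjusted rate optional without a rule, while treatment to radiographic progression and HR 0.65 predict about 23–31% longer mean exposure on darolutamide if the trial succeeds. For an AE that the drug does not affect, with a roughly constant hazard, crude incidence would look about 1.15 to 1.25 times higher on darolutamide. The highest value in the table is 1.30, for a 5% 12-month risk with no drop-out. In absolute terms, with the plan's drop-out, this is about 1 to 7 percentage points.

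These figures rest on exponential progression, the accrual projection, assumed AE rates, and treatment ending only at progression, at the competing hazard shown or at data cut-off. The primary analysis is unaffected, and a reader of the report would see the exposure imbalance. What might be missing is the AE comparison that allows for it.

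**What to change.** In Section 10.3.3, delete the condition on the exposure-adjusted summary and mirror the change in the Protocol summary. Beside crude incidence, always report by arm, for grade 3 or higher AEs, SAEs and the risks named in Section 1.4.1:
- **First-event rate:** patients with a first event divided by time at risk, counted from first dose to first event or the end of the AE window, with the same window for numerator and denominator. This also settles the minor 30-day alignment.
- **Cumulative incidence curves:** Aalen-Johansen estimates with death as a competing event. They are needed because a single rate assumes a constant hazard; for early-onset AEs, the longer exposure on darolutamide would dilute its rate.

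Keep the total-event rate per 100 subject-years as a descriptive extra.

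The change uses data already collected and alters no treatment or visit rule. About 115 of 300 patients were enrolled at the current amendment, so it can still be prespecified before the 138-event interim analysis. The cost is some wording and a slightly longer safety output.

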**Table 3. Safety Laboratory Analyses to be Performed During the Trial**

Haematology 	Serum chemistry 
Haemoglobin	ALAT
Haematocrit	Albumin
Platelet count	Alkaline phosphatase
Red Blood Cell Count	ASAT
WBC (total and differential)	Blood urea nitrogen
ANC	Calcium
Lymphocytes	Chloride
	C-reactive protein
	Creatinine 
	Direct Bilirubin 
	GGT
	Glucose
	LDH
	Magnesium
	Phosphorus
	Potassium
	Sodium
	Total Bilirubin
	Total protein
	Urea
	Uric Acid

ALAT= Alanine aminotransferase, ASAT=Aspartate aminotransferase, ANC= Absolute Neutrophil Count GGT= gamma-glutamyl transferase, LDH= Lactate dehydrogenase, PSA= Prostate specific antigen, WBC= White blood cell

(1) To be performed at screening visit (within 7 days prior to the first administration of study treatment) and at each subsequent clinical visit. For subsequent visits, blood draw is to be performed within 2 days before the date of the visit.

(2) With estimated GFR (MDRD or CKI EPI method)

(3) If total bilirubin is elevated above the upper limit of normal

**Note:** Investigators should ensure that all study enrolment criteria have been met at randomisation. If a patient's status changes (including laboratory results or receipt of additional medical records) during the screening period prior to randomisation such that he no longer meets all eligibility criteria, then the patient should be excluded from participation in the study. Patients who fail to meet the inclusion and exclusion criteria (i.e., screen failures) may be rescreened once, if their condition changes. Rescreening must be discussed with and approved by the sponsor on a case-by-case basis. Patients who are determined to be eligible for rescreening must reconsent and will then be assigned a new screening number.

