#### 7.3.2. Visit 2 - Day 30 (±3 days)

The following should be performed:

- Complete clinical examination (major body systems).
- Collection of height and body weight.
- Measurement of vital signs (blood pressure, seated heart rate, body temperature).
- Assessment of ECOG performance status.
- Assessment of ongoing toxicities including pre-existing symptoms and any concomitant therapies received.
- Haematology analysis (see Table 3, page 47).
- Serum chemistry (see Table 3, page 47).
- Measurement of serum PSA and testosterone levels.
- **French Investigational sites only – For patients who provide additional informed consent:** Collection of blood samples for translational analyses (see Section 9.1.1).
- **Patients who provide additional informed consent:** Abdominal circumference, body mass index (BMI) and maximum handgrip strength using a hand dynamometer. Handgrip strength should be measured twice.

---

 Blood draw may be performed up to 48 hours prior to the visit date

- Dispensation of treatment for 30 days.

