#### 7.3.7. Subsequent Visits

Additional clinical visits are to be performed every 120 ( $\pm 14$ ) days during the first 2 years of treatment, and then every 180 ( $\pm 14$ ) days, until the end of study treatment.

The following should be performed:

- Complete clinical examination (major body systems).
- Collection of height and body weight.
- Measurement of vital signs (blood pressure, seated heart rate, body temperature).
- Assessment of ECOG performance status.
- Electrocardiogram (only in case of abnormal results at screening visit, or if clinically indicated by patient symptoms)

---

 Blood draw may be performed up to 48 hours prior to the visit date

- Assessment of ongoing toxicities including pre-existing symptoms and any concomitant therapies received.
- Haematology analysis (see Table 3, page 47).
- Serum chemistry (see Table 3, page 47).
- Measurement of serum PSA and testosterone levels.
- Assessment of patient quality of life using the following tools:
  - EORTC-QLQ-C30 (Appendix 10)
  - EORTC-QLQ-PR25 (Appendix 11)
  - BPI-SF (Appendix 12).
- Assessment of patient geriatric status using the G-CODE assessment tool (Appendix 8).
- Disease evaluation (see Section 7.3.8).
- **Patients who provide additional informed consent:** Abdominal circumference, body mass index (BMI) and maximum handgrip strength using a hand dynamometer. Handgrip strength should be measured twice.
- Dispensation of sufficient treatment until the next scheduled study visit.

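### The single pooled adverse-event rate in section 10.3.3 does not by itself allow for longer treatment in one arm when visits thin out; rates by period of treatment should be added

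*Protocol*

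**What the plan says.** Section 10.3.3 gives "Incidence of AEs will be summarized by system organ class and preferred term according to MedDRA coding", by arm and by worst grade. It adds, as the allowance for unequal treatment length, "an additional summary based on event rate per 100-subject years of treatment duration will also be summarized, if necessary". The rate is the "total number of treatment emergent events divided by the total treatment duration per 100-subject years". Treatment duration is "date of the last dose of any study treatment – date of the first dose of any study treatment + 1".

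Sections 7.3.2 to 7.3.6 place on-treatment visits at days 30, 60, 120, 180 and 240. Section 7.3.7 continues every 120 "days during the first 2 years of treatment, and then every 180" days. Toxicity review is a procedure at each of these visits. Table 3 requires safety bloods at screening "and at each subsequent clinical visit". Treatment runs to radiographic progression (section 7). Section 8.1.3 has all adverse events recorded from consent "until 30 days after the last dose of IMP", and section 8.1.2 asks for start and end dates.

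**The concern.** The rate exists for the case in which the arms are treated for different lengths of time. A ratio of all events to all time corrects for that only if a month of treatment in year three yields as many recorded events, on average, as a month in the first half-year. The visit calendar puts that in doubt for anything found only when blood is drawn. It is also in doubt for toxicity that clusters early or late. If darolutamide delays progression as hypothesised, its arm holds more late, sparsely observed patient-time.

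Safety is a key secondary objective (section 2.2), and acceptable toxicity in frail men is part of the rationale (section 1.2). Section 1.4.1 lists decreased neutrophils, raised bilirubin and raised ASAT as laboratory findings related to darolutamide, so events that depend on blood draws matter here. This is also the only exposure adjustment that section 10.3.3 specifies.

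**Working it through.** **Inputs.** Visit days are from sections 7.3.2 to 7.3.7. Medians of 12 and 18.5 months, HR 0.65, 85% power, two-sided 0.05, 197 events, the accrual table (18, 50, 53, 179) and the cut at month 75 are from section 10.1. *Assumption:* time on treatment is exponential with the rPFS medians. The protocol gives no adverse-event rate and no capture share, so these are shown as ranges.

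**Design figures.** 12/0.65 = 18.46, the stated 18.5 months. Required events are 194 (Schoenfeld) or 200 (Freedman), and 197 events give 85.6% power. The medians and the event count agree with each other.

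**Visit density.**
- Days 1-240: 5/240 × 365.25 = 7.6 per year
- Days 241-720: 4/480 × 365.25 = 3.0 per year
- Beyond day 720: 365.25/180 = 2.0 per year

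**Patient-time** (simulated with the accrual table and the month-75 cut):

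| | Control | Darolutamide |
|---|---|---|
| Mean time on treatment, months | 14.6 | 19.2 |
| Share in days 1-240 | 43% | 36% |
| Share beyond day 720 | 14% | 20% |
| Scheduled visits per 100 patient-years | 461 | 422 |

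**Events found only at visits.** The visit ratio is 422/461 = 0.92. An asymptomatic abnormality lasting 30 days (an assumed length) is caught with probability visits per year × 30/365.25. That is 37.8% against 34.7%, again 0.92. A dropout hazard of 0.014, read as monthly, gives 0.93. Counting end-of-treatment visits without dropout gives 0.88. If instead patients are followed without staggered entry, the ratio is 0.86, with a range of 0.83 to 0.89 across end-of-treatment visit, cut-off and dropout variants.

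**Partial capture.** If a share f of events is recorded whatever the spacing, the ratio is f + (1 − f) × 0.92. This gives 0.96 at f = 0.5, 0.98 at 0.75, 0.99 at 0.9 and 1.00 at 1. Starting from 0.86, the first three are 0.93, 0.96 and 0.99.

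**Front-loaded toxicity, full capture.** Let the true rate be k times higher in days 1-240, which hold a share s of the time (0.434 and 0.356). The pooled rate is proportional to 1 + (k − 1)s.
- k = 2: 1.356/1.434 = 0.95
- k = 3: 1.712/1.868 = 0.92

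**Late-rising toxicity, full capture.** Let the rate after day 240 be k times the earlier one. The pooled rate is proportional to s + k(1 − s).
- k = 1.5: 1.322/1.283 = 1.03
- k = 2: 1.644/1.566 = 1.05

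**Thirty-day window.** Suppose events are counted to 30 days after the last dose while the denominator stops at the last dose. Mean treatment is 12/ln 2 = 17.3 months (527 days) and 18.5/ln 2 = 26.7 months (812 days). The rate is inflated by 30/527 = 5.7% and 30/812 = 3.7%, so the ratio moves by 1.037/1.057 = 0.98.

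**Does splitting help?** Without staggered entry, visits per patient-year (control, darolutamide) are 7.54 and 7.56 to day 240, 2.71 and 2.82 to day 720, and 1.70 and 1.81 after. The ratios are 1.00, 1.04 and 1.07, against 0.86 pooled on the same assumptions. The schedule effect disappears early on. A smaller one, of opposite sign, remains later.

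**The case against.** The strongest reply is that adverse events are not captured only at visits. All must be recorded up to 30 days after the last dose, with dates, so a symptomatic event between visits is reported late but still counted. Serious events are notified within 24 hours of knowledge (section 8.2.2), and section 6.2 provides for reports from patient, relative or general practitioner in an emergency. Both arms follow the same calendar, under blinding. This stands: with full capture and a constant true rate the ratio is 1.00. It does not cover transient asymptomatic laboratory changes, which go unseen if no blood is drawn, and it does not touch a true rate that changes over time.

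A reader might infer that the formula favours darolutamide by construction, or that the fall from 7.6 to 2.0 visits per year implies a nearly fourfold distortion. The documents support neither. The direction depends on the time course: section 1.4.1 also names potential risks such as fractures and muscle loss, which may build up with treatment and would push the ratio above 1. Even with capture tied wholly to visits, the effect is about 8% under the planned accrual and at most 17% in the variants tried.

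It is also fair that the rate is an additional summary made only if needed, beside incidence tables and listings, with no test or stopping rule attached. Events per 100 patient-years is a standard descriptive measure. Finally, the protocol gives no day window for treatment-emergent events, so the 30-day mismatch is only possible; that definition can properly sit in the SAP.

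**Conclusion.** The point holds in a limited form. The protocol fixes a single pooled rate as its allowance for unequal exposure, and in the very situation that calls for it the rate can mislead. With no true difference, the ratio would be about 0.92 to 0.95 for visit-dependent or front-loaded events, 1.00 under a constant rate with full capture, and 1.03 to 1.05 for late-rising toxicity. A window mismatch, if there is one, would add about 2%. These figures rest on exponential time on treatment with the design medians; if the arms are treated for similar lengths of time, the effect largely vanishes. No efficacy conclusion or formal safety decision is affected. This is a cheap improvement to a descriptive summary.

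**What to change.** In section 10.3.3, keep the overall rate and add event rates by arm within periods of broadly constant visit spacing: days 1-240, 241-720 and beyond 720. State that comparison of exposure-adjusted rates between arms rests on the within-period figures, with no single period named as the main result. Promoting days 1-240 to that role would sideline late toxicity. State also that the later periods contain only patients still on treatment, a selection that may differ between arms. Use one window both for counting treatment-emergent events and for time at risk.

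No new data are needed, because adverse events are already dated. The cost is a few more descriptive tables, with small numbers in the later periods.
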